3.13. Source Data Recorded on the Case Report Form

All patient data must have supportive original source documentation in the medical records, or equivalent, before they are transcribed onto the CRF. Data may not be recorded directly onto the CRF and considered as source data unless the sponsor provides written instructions specifying which data are permitted to be recorded directly onto the CRF.

Source data, including test results and/or assessments (eg, clinical laboratory, central ECG evaluation center, and electronic headache diary data) collected by other institutions outside of the study center, are sent to the investigational center where they are retained but not entered into the CRF unless otherwise noted in the protocol. These data may also be sent electronically to the sponsor (or organization performing data management) for direct entry into the clinical database (see Section [13.1](#)). All data from other institutions will be available to the investigator.

The CRFs are filed in the sponsor's central file.

3.14. Study Procedures

Study procedures and assessments with their timing are summarized in [Table 1](#) (patients rolling over from the pivotal efficacy studies), [Table 2](#) (patients not rolling over from the pivotal efficacy studies), and [Table 3](#) (patients rolling over from the pivotal efficacy studies for ADA assessment only). Detailed by-visit information is provided in the sections following the table. Detailed descriptions of each assessment are provided in Section [6](#) (efficacy assessments), Section [7](#) (safety assessments), and Section [8](#) (pharmacokinetic and other assessments).

Table 1: Study Procedures and Assessments for Patients Rolling Over from the Pivotal Efficacy Studies

Study period	Pre-treatment period ^a	Treatment period													Follow-up period
		V1	V2 ^b	V3	V4	V5	V6	V7	V8	V9	V10	V11	V12	V13	
Procedures and assessments (completed before dosing, when applicable, unless otherwise noted)	Screening days -28 to -1	Dose 1 day 0 (±5 days)	Dose 2 day 28 (±5 days)	Dose 3 day 56 (±5 days)	Dose 4 day 84 (±5 days)	Dose 5 day 112 (±5 days)	Dose 6 day 140 (±5 days)	Dose 7 day 168 (±5 days)	Dose 8 day 196 (±5 days)	Dose 9 day 224 (±5 days)	Dose 10 day 252 (±5 days)	Dose 11 day 280 (±5 days)	Dose 12 day 308 (±5 days)	EOT/early withdrawal day 336 (±5 days)	Final visit day 533 (±15 days)
Informed consent		X													
Inclusion and exclusion criteria		X													
Randomization ^c		X													
Full physical examination, including weight		X ^d					X	X					X	X	X
12-lead ECG ^e		X ^d												X	
Vital signs measurement ^e		X ^d	X	X	X	X	X	X	X	X	X	X	X	X	
Clinical laboratory tests ^f		X ^d		X		X		X		X		X		X	
Urine β-HCG test ^g		X ^d	X	X	X	X	X	X	X	X	X	X	X	X	
Adverse events ^h		X ⁱ	X	X	X	X	X	X	X	X	X	X	X	X	X
Concomitant medication inquiry		X ^j	X	X	X	X	X	X	X	X	X	X	X	X	X ^k
eC-SSRS ^l		X ^d	X	X	X	X	X	X	X	X	X	X	X	X	X
Provide electronic headache diary device		X					X						X		
Complete electronic headache diary entries ^m		X	—————X				X	—X					X	—X	
Review electronic headache diary			X	X	X			X						X	
Return electronic headache diary device					X			X						X	

Clinical Study Protocol with Amendment 01

Study period	Pre-treatment period ^a	Treatment period													Follow-up period
		V1	V2 ^b	V3	V4	V5	V6	V7	V8	V9	V10	V11	V12	V13	
Procedures and assessments (completed before dosing, when applicable, unless otherwise noted)	Screening days -28 to -1	Dose 1 day 0 (±5 days)	Dose 2 day 28 (±5 days)	Dose 3 day 56 (±5 days)	Dose 4 day 84 (±5 days)	Dose 5 day 112 (±5 days)	Dose 6 day 140 (±5 days)	Dose 7 day 168 (±5 days)	Dose 8 day 196 (±5 days)	Dose 9 day 224 (±5 days)	Dose 10 day 252 (±5 days)	Dose 11 day 280 (±5 days)	Dose 12 day 308 (±5 days)	EOT/early withdrawal day 336 (±5 days)	Final visit day 533 (±15 days)
Blood samples for plasma drug concentration					X			X			X			X	X
Blood samples for serum ADA assessment ⁿ					X			X						X	X
Blood sample for pharmacogenomic analysis ^o		X													
Blood collection for serum, plasma, and RNA biomarker analysis								X						X	X
Urine collection for biomarker analysis								X						X	X
HIT-6 ^p								X						X	
MIDAS questionnaire ^q								X						X	
PHQ-2/PHQ-9 ^r								X						X	
MSQOL questionnaire								X						X	
EQ-5D-5L questionnaire								X						X	
PGIC scale			X		X			X			X			X	
WPAI questionnaire								X						X	
Administer study drug injection		X	X	X	X	X	X	X	X	X	X	X	X		
Injection site assessments ^s		X	X	X	X	X	X	X	X	X	X	X	X		

^a The pretreatment period refers to the screening visit and 28-day run-in period of the pivotal efficacy studies (Studies TV48125-CNS-30049 and TV48125-CNS-30050).

Clinical Study Protocol with Amendment 01

- ^b Patients rolling over from the pivotal efficacy studies will begin study participation at visit 2. If visit 2 corresponds with EOT visit (visit 5) of the pivotal efficacy study, the EOT visit procedures/assessments for the pivotal efficacy study must be completed before the patient begins participation in this study, and the EOT procedures/assessments will not be repeated at visit 2. Refer to the protocols for Studies TV48125-CNS-30049 and TV48125-CNS-30050 for details regarding the EOT visit procedures/assessments.
- ^c Patients who received placebo in the pivotal efficacy studies will be randomized to receive 1 of 3 TEV-48125 dose regimens (a loading dose of TEV-48125 at 675 mg followed by monthly TEV-48125 at 225 mg [CM only], monthly TEV-48125 at 225 mg, or quarterly TEV-48125 at 675 mg).
- ^d Procedure/assessment will only be completed for patients who enter this study more than 30 days after completing visit 5 of the pivotal efficacy study.
- ^e Procedure/assessment will be performed before other assessments (eg, blood draws and administration of questionnaires).
- ^f Serum chemistry, hematology, coagulation, and urinalysis.
- ^g Women of childbearing potential only.
- ^h Inquiries about adverse events will be made at every visit. At visits 2 through 13, inquiries about adverse events will be made before and after study drug administration. Postdose inquiries will be made before the patient leaves the study center.
- ⁱ The predose adverse event inquiry will only be completed for patients who begin this study on a different day from the EOT visit of the pivotal efficacy study.
- ^j Procedure/assessment will only be completed for patients who begin this study on a different day from the EOT visit of the pivotal efficacy study.
- ^k As appropriate, patients should be treated with standard of care following completion of the EOT/early withdrawal visit.
- ^l The eC-SSRS Since Last Visit version will be completed.
- ^m Patients will complete electronic headache diary entries about the previous day daily (beginning on day 1) during the first 3 months, during the 4-week period after visit 7, and during the 4-week period after visit 13.
- ⁿ Blood samples for serum ADA assessment will also be collected upon observation of any severe hypersensitivity reaction (eg, anaphylaxis).
- ^o A single blood sample for pharmacogenomic analysis will be collected at visit 2 of the pivotal efficacy study or any visit thereafter from patients who consent to pharmacogenomic analyses, if the sample is not obtained during their participation in Studies TV48125-CNS-30049 or TV48125-CNS-30050. A separate informed consent form for pharmacogenomic sampling must be signed by the patient.
- ^p The HIT-6 will only be administered to patients with CM.
- ^q The MIDAS questionnaire will only be administered to patients with EM.
- ^r Patients will respond first to the PHQ-2. They will respond to questions 3 through 9 (unique questions) of the PHQ-9 only if PHQ-2 is positive.
- ^s Injection site assessments will be performed immediately and 1 hour after study drug administration. If a patient has severe injection site induration, erythema, and/or ecchymosis and/or grade 3 (severe) or grade 4 (worst possible) injection site pain at 1 hour after completion of study drug administration, the patient will be reassessed at 3 hours after study drug administration and hourly thereafter until the reaction/pain is of moderate or less severity.

ADA=antidrug antibody; β -HCG=beta-human chorionic gonadotropin; ECG=electrocardiogram; eC-SSRS=electronic Columbia-Suicide Severity Rating Scale; EOT=end-of-treatment; EQ-5D-5L=EuroQol-5 Dimension, 5 response level version; FSH=follicle-stimulating hormone; HIT-6=6-item Headache Impact Test; MIDAS=Migraine Disability Assessment; MSQOL=Migraine-Specific Quality of Life; PGIC=Patient Global Impression of Change; PHQ-2=2-item Patient Health Questionnaire; PHQ-9=9-item Patient Health Questionnaire; V=visit; WPAI=Work Performance and Activity Impairment.

Table 2: Study Procedures and Assessments for Patients Not Rolling Over from the Pivotal Efficacy Studies

Study period	Pre-treatment period ^a	Treatment period													Follow-up period
		V1	V2	V3	V4	V5	V6	V7	V8	V9	V10	V11	V12	V13	
Procedures and assessments (completed before dosing, when applicable, unless otherwise noted)	Screening days -28 to -1	Dose 1 day 0 (+ 5 days)	Dose 2 day 28 (±5 days)	Dose 3 day 56 (±5 days)	Dose 4 day 84 (±5 days)	Dose 5 day 112 (±5 days)	Dose 6 day 140 (±5 days)	Dose 7 day 168 (±5 days)	Dose 8 day 196 (±5 days)	Dose 9 day 224 (±5 days)	Dose 10 day 252 (±5 days)	Dose 11 day 280 (±5 days)	Dose 12 day 308 (±5 days)	EOT/early withdrawal day 336 (±5 days)	Final visit day 533 (±15 days)
Informed consent	X														
Medical and psychiatric history	X														
Prior medication history	X														
Record demographic characteristics	X														
Inclusion and exclusion criteria	X	X													
Randomization ^b		X													
Physical examination, including weight/height ^c	X	X	X	X	X		X	X					X	X	X
12-lead ECG ^{d,e}	X	X												X	
Vital signs measurement ^d	X	X	X	X	X	X	X	X	X	X	X	X	X	X	
Clinical laboratory tests ^f	X	X		X		X		X		X		X		X	
Serum β-HCG test ^g	X														
Urine β-HCG test ^g		X	X	X	X	X	X	X	X	X	X	X	X	X	
FSH ^h	X														
Adverse events ^{e,i}	X	X	X	X	X	X	X	X	X	X	X	X	X	X	X
Concomitant medication inquiry ^e	X	X	X	X	X	X	X	X	X	X	X	X	X	X	X ^j

Clinical Study Protocol with Amendment 01

Study period	Pre-treatment period ^a	Treatment period													Follow-up period
		V1	V2	V3	V4	V5	V6	V7	V8	V9	V10	V11	V12	V13	
Procedures and assessments (completed before dosing, when applicable, unless otherwise noted)	Screening days -28 to -1	Dose 1 day 0 (+ 5 days)	Dose 2 day 28 (±5 days)	Dose 3 day 56 (±5 days)	Dose 4 day 84 (±5 days)	Dose 5 day 112 (±5 days)	Dose 6 day 140 (±5 days)	Dose 7 day 168 (±5 days)	Dose 8 day 196 (±5 days)	Dose 9 day 224 (±5 days)	Dose 10 day 252 (±5 days)	Dose 11 day 280 (±5 days)	Dose 12 day 308 (±5 days)	EOT/early withdrawal day 336 (±5 days)	Final visit day 533 (±15 days)
eC-SSRS ^k		X	X	X	X	X	X	X	X	X	X	X	X	X	X
Provide electronic headache diary device ^l	X						X						X		
Complete electronic headache diary entries ^m	X				X		X	X					X	X	
Review electronic headache diary		X	X	X	X			X						X	
Return electronic headache diary device					X			X						X	
Blood samples for plasma drug concentration ^e		X			X			X			X			X	X
Blood samples for serum ADA assessment ⁿ		X			X			X						X	X
Blood sample for pharmacogenomic analysis ^o		X													
Blood collection for serum, plasma, and RNA biomarker analysis		X						X						X	X
Urine collection for biomarker analysis		X						X						X	X
HIT-6 ^p		X						X						X	
MIDAS questionnaire ^q		X						X						X	
PHQ-2/PHQ-9 ^r		X						X						X	

Clinical Study Protocol with Amendment 01

Study period	Pre-treatment period ^a	Treatment period													Follow-up period
		Visit number	V1	V2	V3	V4	V5	V6	V7	V8	V9	V10	V11	V12	
Procedures and assessments (completed before dosing, when applicable, unless otherwise noted)	Screening days -28 to -1	Dose 1 day 0 (+ 5 days)	Dose 2 day 28 (±5 days)	Dose 3 day 56 (±5 days)	Dose 4 day 84 (±5 days)	Dose 5 day 112 (±5 days)	Dose 6 day 140 (±5 days)	Dose 7 day 168 (±5 days)	Dose 8 day 196 (±5 days)	Dose 9 day 224 (±5 days)	Dose 10 day 252 (±5 days)	Dose 11 day 280 (±5 days)	Dose 12 day 308 (±5 days)	EOT/early withdrawal day 336 (±5 days)	Final visit day 533 (±15 days)
MSQOL questionnaire		X						X						X	
EQ-5D-5L questionnaire		X						X						X	
PGIC scale			X		X			X			X			X	
WPAI questionnaire		X						X						X	
Administer study drug injection		X	X	X	X	X	X	X	X	X	X	X	X		
Injection site assessments ^s		X	X	X	X	X	X	X	X	X	X	X	X		

^a The pretreatment period includes the screening visit and the 28-day run-in period.

^b Eligible patients will be randomized to receive 1 of 3 TEV-48125 dose regimens (a loading dose of TEV-48125 at 675 mg followed by monthly TEV-48125 at 225 mg [CM only], monthly TEV-48125 at 225 mg, or quarterly TEV-48125 at 675 mg).

^c Height will only be obtained at screening.

^d Procedure/assessment will be performed before other assessments (eg, blood draws and administration of questionnaires).

^e Patients will return to the study center for up to 2 additional visits after any dose of study drug for blood sampling for plasma TEV-48125 concentration determination, triplicate 12-lead ECGs, and inquiries about adverse events and concomitant medications. These visits should occur during the following time periods relative to any dose of study drug: 3 to 10 days or 15 to 20 days after study drug administration.

^f Serum chemistry, hematology, coagulation, and urinalysis.

^g Women of childbearing potential only; a serum β-HCG test will be performed at screening, and urine β-HCG tests will be performed at subsequent visits.

^h Postmenopausal women only.

ⁱ Inquiries about adverse events will be made at every visit. At visits 2 through 13, inquiries about adverse events will be made before and after study drug administration. Postdose inquiries will be made before the patient leaves the study center.

^j As appropriate, patients should be treated with standard of care following completion of the EOT/early withdrawal visit.

^k The eC-SSRS Baseline/Screening version will be completed at visit 2, and the eC-SSRS Since Last Visit version will be completed at all other visits.

^l Eligible patients will be given an electronic headache diary device and will be trained in its use and compliance requirements on the day of screening.

^m Patients will complete electronic headache diary entries about the previous day daily (beginning on day -27) during the first 4 months, during the 4-week period after visit 7, and during the 4-week period after visit 13.

ⁿ Blood samples for serum ADA assessment will also be collected upon observation of any severe hypersensitivity reaction (eg, anaphylaxis).

^o A single blood sample for pharmacogenomic analysis will be collected at visit 2 or any other visit thereafter from patients who consent to pharmacogenomic analyses, if the sample is not obtained during their participation in Studies TV48125-CNS-30049 or TV48125-CNS-30050. A separate informed consent form for pharmacogenomic sampling must be signed by the patient.

Clinical Study Protocol with Amendment 01

^p The HIT-6 will only be administered to patients with CM.

^q The MIDAS questionnaire will only be administered to patients with EM.

^r Patients will respond first to the PHQ-2. They will respond to questions 3 through 9 (unique questions) of the PHQ-9 only if PHQ-2 is positive.

^s Injection site assessments will be performed immediately and 1 hour after study drug administration. If a patient has severe injection site induration, erythema, and/or ecchymosis and/or grade 3 (severe) or grade 4 (worst possible) injection site pain at 1 hour after completion of study drug administration, the patient will be reassessed at 3 hours after study drug administration and hourly thereafter until the reaction/pain is of moderate or less severity.

ADA=antidrug antibody; β -HCG=beta-human chorionic gonadotropin; ECG=electrocardiogram; eC-SSRS=electronic Columbia Suicide Severity Rating Scale; EOT=end-of-treatment; EQ-5D-5L=EuroQol-5 Dimension, 5 response level version; FSH=follicle-stimulating hormone; HIT-6=6-item Headache Impact Test; MIDAS=Migraine Disability Assessment; MSQOL=Migraine-Specific Quality of Life; PGIC=Patient Global Impression of Change; PHQ-2=2-item Patient Health Questionnaire; PHQ-9=9-item Patient Health Questionnaire; V=visit; WPAI=Work Performance and Activity Impairment.

Table 3: Study Procedures and Assessments for Patients Rolling Over from the Pivotal Efficacy Studies for Antidrug Antibody Assessment Only

	Enrollment visit	Follow-up visit
Visit number	V2 ^a	V16 (ADA collection)
Procedures and assessments	Day 0	Approximately 7.5 months (225±15 days) after the last dose of study drug during the pivotal efficacy study
Informed consent	X	
Adverse events	X	X
Concomitant medication inquiry	X	X
Blood sample for serum ADA assessment		X

^a If visit 2 corresponds with EOT visit/early withdrawal visit of the pivotal efficacy study, the EOT visit procedures/assessments for the pivotal efficacy study must be completed before the patient begins participation in this study, and the EOT procedures/assessments will not be repeated at visit 2.
ADA=antidrug antibody; EOT=end of treatment; V=visit.

3.14.1. Procedures for Screening of Patients Not Rolling Over from the Pivotal Efficacy Studies (Visit 1 [Day -28])

Patients not rolling over from the pivotal efficacy studies will be screened approximately 28 days before the baseline visit.

A signed and dated informed consent form will be obtained before screening procedures commence (see Section 12.1). Evaluations obtained as part of routine medical care and performed during the screening period may be used in place of the protocol-specific evaluations. In addition, disease-specific assessments performed within a specified time frame before informed consent may be used for the study. Patients will acknowledge and agree to the possible use of this information for the study by giving informed consent.

After informed consent is obtained, patients who are screened will be assigned an 8-digit identification number such that all patients from each country are given consecutive identification numbers in successive order of inclusion. The first 2 digits of the screening number will be the number assigned to the country where the investigational center is located, the next 3 digits will be the investigational center number, and the last 3 digits will be the patient number assigned at the investigator center (eg, the 3rd patient screened in the US [country 01] at center 101 would be given the number of 01101003). The screening number is the permanent number assigned to the patient for the duration of study.

After confirmation of study eligibility, patients will be screen failed or randomized into the current study. For randomized patients, an enrollment number will be assigned consisting of the 8-digit screening number for randomized patients and the last 2 digits of the assigned protocol (ie, 51 for Study TV48125-CNS-30051).

A patient who is screened and does not meet study entry criteria will not be considered for screening again.

The following procedures will be performed at visit 1:

- Obtain written informed consent before any other study-related procedures are performed.
- Review inclusion/exclusion criteria.
- Review medical and psychiatric history.
- Review medication history.
- Record demographic characteristics including race.
- Perform vital signs measurements (includes systolic and diastolic blood pressure, pulse, body temperature, and respiratory rate).
- Perform 12-lead ECG.
- Perform physical examination, including weight and height. Body mass index will be calculated.
- Perform clinical laboratory tests (serum chemistry, hematology, coagulation, and urinalysis).
- Perform serum β -HCG test (women of childbearing potential only).
- Perform FSH (postmenopausal women only).

Patients who meet inclusion/exclusion criteria will be given an electronic headache diary device and instructed in its use and compliance requirements.

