Patients who rollover from the pivotal efficacy studies and are eligible to participate in this study will begin this study at visit 2 after completing the informed consent process. Visit 2 may correspond with the end-of-treatment (EOT) visit (visit 5) or it may be a separate visit. For patients who begin this study on the same day as EOT visit (visit 5) for the pivotal efficacy studies, EOT visit procedures/assessments must be completed before beginning visit 2 procedures/assessments. Baseline for patients rolling over from the pivotal efficacy studies refers to the 28-day run-in period (for headache variables only) and visit 2 (day 0) of the pivotal efficacy studies.

Patients randomized to the active treatment groups in the pivotal efficacy studies who continue receiving study drug in the current study will receive the same treatment throughout the current study. Thus, patients with CM who received a loading dose of TEV-48125 at 675 mg followed by monthly sc TEV-48125 at 225 mg and patients with EM who received monthly sc TEV-48125 at 225 mg will continue receiving monthly sc TEV-48125 at 225 mg, and patients with CM or EM who received sc TEV-48125 at 675 mg once in 3 months will continue receiving quarterly sc TEV-48125 at 675 mg.

Patients with CM randomized to the placebo treatment group in the pivotal efficacy study who continue receiving study drug in the current study and patients with CM who are not rolling over from the pivotal efficacy study will be randomized at visit 2 in a 1:1 ratio to receive 1 of 2 treatments:

- sc TEV-48125 at 675 mg (loading dose) followed by 11 monthly sc doses of TEV-48125 at 225 mg
- sc TEV-48125 at 675 mg once every 3 months for 12 months for a total of 4 doses

Patients with EM randomized to the placebo treatment group in the pivotal efficacy study who continue receiving study drug in the current study and patients with EM who are not rolling over from the pivotal efficacy study will be randomized at visit 2 in a 1:1 ratio to receive 1 of 2 treatments:

- monthly sc TEV-48125 at 225 mg for 12 months
- sc TEV-48125 at 675 mg once every 3 months for 12 months for a total of 4 doses

(Note: For this study and the pivotal efficacy studies, monthly dosing refers to dosing approximately every 4 weeks [28 days].)

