3.11. Duration of Patient Participation and Justification

This study will consist of a 28-day run-in period (only for patients not rolling over from the pivotal efficacy studies) and a 12-month treatment period. Patients will be followed for 7.5 months (225 days) after administration of the final dose of study drug (ie, a 6.5-month follow-up period) for collection of pharmacokinetic, immunogenicity, and biomarker samples and inquiries about adverse events and concomitant medication use. It is considered that, with a half-life of around 45 days, there will be a complete washout of the drug from the circulating blood in 7.5 months (≥ 5 half-lives), allowing a more precise evaluation of ADA.

Patients are expected to participate in this study for its entire duration, which is a minimum of 18.5 months for patients rolling over from the pivotal efficacy studies or 19.5 months for patients not rolling over from the pivotal efficacy studies. In addition, patients rolling over from the pivotal efficacy studies for ADA evaluation only will participate in the current study for approximately 7.5 months. See Section 12.4 for the definition of the end of the study.

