3.14.2.2. Patients Rolling Over from the Pivotal Efficacy Studies (Visit 2 [Day 0])

After completing all EOT visit procedures for the pivotal efficacy studies, patients who provide informed consent and meet eligibility requirements will be enrolled into this long-term safety, tolerability, and efficacy study. These patients will retain their screening and enrollment numbers from the pivotal efficacy studies, and they will be assigned a new randomization number generated by the IRT. This newly assigned number will be entered into the CRF.

Patients rolling over from the pivotal efficacy studies will begin this study at visit 2. If visit 2 corresponds with the EOT visit (visit 5) of the pivotal efficacy study, then EOT visit procedures/assessments must be completed before the patient begins participation in this study. The EOT visit procedures/assessments are detailed in the protocols for Studies TV48125-CNS-30049 and TV48125-CNS-30050.

The following procedures will be performed before study drug administration for patients who enroll in the current study on a different day from the EOT visit, but within 30 days:

- Inquire about adverse events.
- Inquire about/review concomitant medications.

In addition, a single 6-mL blood sample for pharmacogenomics (DNA) may be obtained from patients who consent to pharmacogenomics analysis if the sample is not obtained during their participation in Studies TV48125-CNS-30049 or TV48125-CNS-30050.

The following procedures will be performed before study drug administration for patients who complete the EOT visit of the pivotal efficacy study and enroll in the current study after more than 30 days:

- Perform vital signs measurements (including systolic and diastolic blood pressure, pulse, body temperature, and respiratory rate).
- Perform 12-lead ECG.
- Perform physical examination, including weight.
- Inquire about adverse events.
- Inquire about/review concomitant medications.
- Complete the eC-SSRS Since Last Visit version.
- Perform clinical laboratory tests (serum chemistry, hematology, coagulation, and urinalysis).
- Perform urine β -HCG test (women of childbearing potential only).

In addition, a single 6-mL blood sample for pharmacogenomics (DNA) may be obtained from patients who consent to pharmacogenomics analysis if the sample is not obtained during their participation in Studies TV48125-CNS-30049 or TV48125-CNS-30050.

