3.14.3.1.2. Visit 3 (Day 28 ± 5 Days/Dose 2)

The following procedures/assessments will be performed before study drug administration at visit 3:

- Review electronic headache diary.
- Review study compliance.
- Perform vital signs measurements (includes systolic and diastolic blood pressure, pulse, body temperature, and respiratory rate).
- Perform physical examination (including weight) for patients not rolling over only.
- Inquire about adverse events.
- Inquire about/review concomitant medications.
- Complete the eC-SSRS Since Last Visit version.
- Perform urine β -HCG test (women of childbearing potential only).
- Administer the PGIC scale.

In addition, a single 6-mL blood sample for pharmacogenomics (DNA) may be obtained from patients who consent to pharmacogenomics analysis if the sample is not obtained at an earlier visit.

Patients will receive sc TEV-48125 at 225 mg or placebo according to their randomization after completing predose procedures/assessments at each study visit. The following procedures/assessments will be performed after dosing:

- Perform local injection site assessment immediately and at 1 hour after completing study drug administration. Additional injection site assessments may be performed based on the severity of any observed injection site reaction. See Section 7.9 for additional details.
- Inquire about postdose adverse events before the patient leaves the study center.

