if of childbearing potential, patients must meet any of the following criteria:
 - Patients must simultaneously use 2 forms of highly effective contraception methods (defined in Section 5.2) with their partners during the entire study period and for 7.5 months after the last dose of study drug.
 - Sexual abstinence is only considered a **highly effective method** if defined as refraining from heterosexual intercourse in the defined period. The reliability of sexual abstinence needs to be evaluated in relation to the duration of the clinical study and the preferred and usual lifestyle of the subject. Periodic abstinence (eg, calendar, ovulation, symptothermal, post-ovulation methods), declaration of abstinence for the duration of a study, and withdrawal are not acceptable methods of contraception.
- h. Female patients of childbearing potential must have a negative serum β -HCG pregnancy test at screening (confirmed by urine dipstick β -HCG pregnancy test at baseline).

- i. The patient demonstrated compliance with the electronic headache diary during the run-in period by entry of headache data on a minimum of 24 out of 28 days (~85% diary compliance)
- j. The patient is in good health as determined by a medical and psychiatric history, medical examination, 12-lead ECG, serum chemistry, hematology, coagulation, and urinalysis.
- k. The patient must be willing and able to comply with study restrictions, to remain at the clinic for the required duration during the study period, and to return to the clinic for the follow up evaluation as specified in this protocol.

Patients Rolling Over from the Pivotal Efficacy Studies for ADA Assessment Only: Patients may be included in this study if they sign and date the informed consent document.

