4.2. Patient Exclusion Criteria

4.2.1. Patients Rolling Over from the Pivotal Efficacy Studies

Patients will be excluded from participating in this study if they meet any of the following criteria:

- a. Any finding that, in the judgment of the investigator, is clinically significantly abnormal, including hematology values, serum chemistry, coagulation tests, or urinalysis (abnormal tests may be repeated for confirmation)
- b. Pregnant or nursing females
- c. Any finding in the baseline 12-lead ECG considered clinically significant in the judgment of the investigator
- d. Compliance with daily diary entry lower than 75% at the last month of the double-blind treatment period of the pivotal efficacy study

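### Rollover women of childbearing potential who enter 1 to 30 days after the pivotal end-of-treatment visit get their first dose with no required same-day pregnancy test

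*Protocol*

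**What the plan says.** Section 3.1 allows a gap between the pivotal study and this one: "Visit 2 may correspond with the end-of-treatment (EOT) visit (visit 5) or it may be a separate visit".

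Table 1 in Section 3.14 schedules a urine β-HCG test for rollover women of childbearing potential at visits 2 to 14. The visit 2 entry alone has a condition, set by footnote d as follows: "Procedure/assessment will only be completed for patients who enter this study more than 30 days after completing visit 5 of the pivotal efficacy study". The same footnote covers the visit 2 physical examination, ECG, vital signs, laboratory tests and eC-SSRS.

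Section 3.14.2.2 repeats the rule as procedure lists. The list "for patients who enroll in the current study on a different day from the EOT visit, but within 30 days" has two items, adverse events and concomitant medications, plus an optional pharmacogenomic sample. The urine test appears only in the list for entry after more than 30 days. For same-day entry, the pivotal EOT assessments stand and are not repeated.

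Pregnancy excludes a rollover patient (Section 4.2.1, criterion b: "Pregnant or nursing females"), but no test is attached to that criterion. For new patients, Section 4.1.2, criterion h, is explicit: "Female patients of childbearing potential must have a negative serum" pregnancy test at screening, and a urine dipstick must confirm it at baseline.

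**The concern.** A site that follows the protocol exactly can give the first dose of a long-acting antibody to a woman who conceived after the EOT visit, because nothing requires a test on the day. The injection cannot be withdrawn, and Section 3.11 describes a drug "with a half-life of around 45 days".

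The clearest case is a woman who had placebo in the pivotal study, for whom visit 2 is the first exposure of all. A woman from an active arm already carries drug, so for her it is one further dose.

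The rule also sits oddly beside others in the same table. Footnote j, on concomitant medication, reads "Procedure/assessment will only be completed for patients who begin this study on a different day from the EOT visit of the pivotal efficacy study", and footnote i says the same of the predose adverse event inquiry. A woman entering on day 20 must be asked about her medications but need not be tested for pregnancy.

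**Working it through.** The plan gives no figure to reproduce. The check sets the requirements side by side and then does simple day arithmetic.

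**Pregnancy test required by this protocol before dosing**

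| Situation | Requirement | Source |
|---|---|---|
| New patient, dose 1 | Serum at screening (about day −28) and urine at visit 2 | 4.1.2 h; Table 2; 3.14.2.1.2 |
| Rollover, entry after more than 30 days, dose 1 | Urine at visit 2 | Table 1 footnote d; 3.14.2.2 |
| Rollover, entry on the EOT day, dose 1 | None separately; that day's EOT assessments stand in | Table 1 footnote b |
| Rollover, entry 1 to 30 days after EOT, dose 1 | None | Table 1 footnote d; 3.14.2.2 |
| Any patient, doses 2 to 12 (visits 3 to 13) | Urine at the same visit, before the dose | Tables 1 and 2; 3.14.3.1.2 to 3.14.3.1.9 |

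Three other places could have closed the gap, and none does:

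- Section 3.14.3.1.1 (visit 2) adds only postdose checks.
- Section 7.3.5.1 refers back to the tables, so footnote d still applies.
- SAP Section 7.6 mentions urine tests at visits 2 through 5 without the 30-day condition. SAP Table 1 nevertheless repeats footnote d, and an analysis plan does not instruct sites.

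Day 30 itself falls in the untested group. For these women, 11 of the 12 dosing visits (2 to 13) have a required predose test; the one without is the first dose in this study.

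**Time from EOT to the next required test**

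The next required test is at visit 3, day 28 ± 5, where the list headed "The following procedures/assessments will be performed before study drug administration at visit 3" includes the urine test. For entry k days after EOT, the interval is k + 23 to k + 33 days:

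- k = 1: 1 + 23 = 24 to 1 + 33 = 34 days
- k = 30: 30 + 23 = 53 to 30 + 33 = 63 days

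The range over the window is 24 to 63 days, with a dose at visit 2 in between. It is an interval between tests only if one was done at the pivotal EOT visit.

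**Drug remaining when that test is done**

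Assume first-order decline from dosing and ignore the absorption phase (median t_max 96 to 108 hours, Section 1.3.2.1). The fraction remaining is 0.5^(t / half-life).

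- 45-day half-life (Section 3.11): 0.5^(28/45) = 0.65 at day 28; 0.70 at day 23; 0.60 at day 33
- Half-lives of 27 to 50 days (Section 1.3.2.1, from the 225-mg and 900-mg dose levels): 0.5^(28/27) = 0.49 to 0.5^(28/50) = 0.68 at day 28

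By the protocol's own 225-day washout, 225 − 28 = 197 days would remain at visit 3. These figures show that the exposure is lasting. They would apply after any dose and do not measure the gap itself.

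**The case against.** The strongest reply is that footnote d is a deliberate, uniform rule. It carries the pivotal EOT assessments forward for 30 days across six safety procedures, and Amendment 01 revisited its wording. If the pivotal EOT visit includes a pregnancy test, the result is at most 30 days old at the first dose, close to the 28-day spacing of later tests. Routine tests can already be 28 + 5 + 5 = 38 days apart under the visit windows, so entry on days 1 to 5 (at most 5 + 33 = 38 days) creates no longer interval than the protocol allows elsewhere.

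Other protections exist too. Eligibility is reviewed at visit 2, different-day entrants are asked about adverse events before dosing, Section 5.2 describes contraception, and pregnancy stops treatment. Section 1.3.1 reports preliminary data with no apparent embryo-fetal toxicity.

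Much of this stands as a limit on weight. The size of the gap depends on pivotal protocols that are not available here, and for early entry the defect is the missing same-day test and not a longer interval. Footnotes i and j govern history-taking, so they supply a ready-made rule more than a precedent for testing.

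The central point survives. Later tests are about 28 days apart, but each comes before that day's dose, which is not so here. Criterion h shows that the sponsor does not rely on a result about four weeks old before a new patient's first dose. Eligibility review and open questions can miss an early, unrecognised pregnancy. A 30-day carry-over may suit an ECG or a physical examination, but pregnancy status can change within that window.

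**Conclusion.** The concern holds. For rollover women of childbearing potential who enter 1 to 30 days after the pivotal EOT visit, no pregnancy test is required at visit 2 before dosing. Table 1 and Section 3.14.2.2 agree, so this is neither a table-reading artefact nor a conflict between sections.

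The gap is one untested dosing visit out of 12. The first required test comes 24 to 63 days after EOT, when about 65% of the visit 2 dose remains if the half-life is 45 days.

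Two things are unknown: whether a test is done at the pivotal EOT visit, and how many women are affected. The documents give neither the share entering on a different day nor the number of childbearing potential. With no embryo-fetal signal in the preliminary data, this is an inconsistently applied precaution. It has no bearing on any endpoint, sample size or analysis. It should be fixed because the remedy is so small.

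**What to change.** On the visit 2 urine β-HCG entry in Protocol Table 1, and in its copy in the SAP, replace footnote d with the different-day rule of footnote j. Add the urine test, for women of childbearing potential, to the within-30-days list in Section 3.14.2.2. Waive it only when the first dose is given on the EOT day and a negative EOT test is on record. Leave the 30-day waiver as it is for the other five procedures.

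All 12 dosing visits would then have a predose test for women entering on a different day. If a test is done at EOT, the longest planned interval between tests around the first dose falls from 63 days (30 + 28 + 5) to 33 days (28 + 5).

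The cost is one footnote letter, one bullet and one dipstick per affected woman at a visit she already attends, with no extra visit, blood draw or staff.

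Two drafting points can be tidied in the same amendment, though the finding does not depend on them: repeat contraception criterion g in Section 4.1.1 for rollover patients, and align SAP Section 7.6 (urine tests at visits 2 through 5) with SAP Tables 1 and 2 (visits 2 through 14).
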